### Parasternal intercostal nerve block

The parasternal blocks will be performed by a blinded surgeon at the end of surgery, just prior to sternal closure.

The medication will be prepared and dispersed by the study pharmacist in a concealed vial. The contents of the vial will be drawn up into two sheathed sterile 30 cc syringes by the operating room staff. Due to the distinct visual characteristics of normal saline (transparent) compared to Exparel® (translucent), sheathed syringes will be used to maintain blinding of the surgeon and operating room staff.

The components of a parasternal nerve block include anesthetizing the anterior cutaneous branches of intercostal nerves two through six and the deep subcutaneous layers around the mediastinal drain sites (Fig. 2). First, sequential intercostal blocks will be performed with 4 mL per intercostal space across 5 intercostal spaces bilaterally. Then 10 mL will be injected in the superficial to deep subcutaneous tissue surrounding mediastinal drains. A total of 50 mL of either 0.9% normal saline or 50 mL of 0.53% Exparel® will be used for the parasternal block.

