## II. CHARACTERISTICS OF THE RESEARCH POPULATION

### Number of subjects.

The study will include 78 patients, 39 patients in the study drug arm and 39 patients in the control arm. Since there are two primary outcomes, we set the type I error at 0.025 for the power analysis. Based on results from a prior study by Barr et al., we assumed a baseline Numerical Rating Scale (NRS) score for pain of 53.2 with standard deviation of 24.1 and a baseline cumulative morphine requirement over 24 hours of 23.2 mg with standard deviation of 8.3 mg. The proposed sample size was calculated to achieve 86% power to detect a 30% decrease in mean NRS scores at the 2.5% level of type I error (two-sided). This sample size also provides for a 98% power to detect a 30% decrease in total opioid consumption over the first 24 hours post-operatively. Note that we assumed the standard deviation decreases accordingly. A 5% drop out rate was included into the sample size calculation.

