### Randomization and Blinding

Patients will be randomized on the day of surgery to either placebo or treatment group. The subjects will be randomized in blocks of 4 to ensure a 1:1 ratio of placebo to treatment groups.

- Placebo: 0.9% normal saline
- Treatment group: 0.53% Exparel®

A randomization sheet will be generated by the study pharmacist, listing the randomization schedule in sequence for each block. The study pharmacist will have control of the randomization sheet. At the time of randomization, he will go to the next available row to determine which medication to dispense. The randomization sheet will document each subject's number, initials, date of surgery and study arm (active or placebo).

The study pharmacist will hold the key identifying which study group corresponds with which letter. In order to maintain blinding of the study investigators, the pharmacist will not reveal the subject's group assignment and data collection will be done according to the subject number. At quarterly intervals during the trial, the study pharmacist will reveal the blinding to the Independent Data/Safety Monitor (DSM) only. This will enable the Independent DSM to capture for any alarming trends in adverse events or serious adverse events as they are occurring. At completion of data collection and analysis for the entire study, the pharmacist will provide the study investigators with a copy of the report revealing which subject belonged to which study group.

The subjects will be blinded to their study arm and remain blinded for the entire duration of this study. Subjects who wish to know which drug they received (Exparel® or placebo), may contact the PI or co-PI and they will be informed of their study group following completion the study.

The study investigators, surgeon administering the medications, operating room staff and ICU/floor staff will all remain blinded. Only the pharmacist who will prepare and dispense the medication will be unblinded.

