#### Assessment of the blind

Subject responses at follow-up regarding speculation about the treatments received will be compared to each subjects actual group assignment in order to determine adequacy of the blind.

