**Table 1: Adverse reactions reported with use of Exparel®**

Incidence	Adverse reaction
Most common (≥ 10%)	Nausea, constipation, vomiting
Common (≥ 2 or ≤ 10%)	Pyrexia, dizziness, peripheral edema, anemia, hypotension, pruritus, tachycardia, headache, insomnia, postoperative anemia, muscle spasm, hemorrhagic anemia, back pain, somnolence, procedural pain
Less common/rare (< 2%)	Chills, erythema, bradycardia, palpitations, supraventricular/ventricular extrasystoles, ventricular tachycardia, anxiety, urinary retention, pain, edema, tremor, postural dizziness, paresthesia, syncope, incision site edema, procedural hypertension/hypotension, procedural nausea, muscular weakness, neck pain, cold sweat, urticaria, confusional state, depression, agitation, hyperhidrosis, restlessness, blurred vision, tinnitus, hypoxia, apnea, urinary incontinence, drug hypersensitivity.

Information reproduced from: *Exparel Prescribing Information*. 23 Jan. 2012. Pacira Pharms, Inc. San Diego, CA.

All parasternal intercostal nerve blocks will be performed by a cardiac surgeon familiar with the study protocol and experienced in performing the procedure. The benefit of performing parasternal blocks prior to sternal closure is the ability to directly visualize and confirm appropriate placement of the needle tip. The syringe will be aspirated prior to injection to avoid intravascular injection of the drug. Hemodynamics and electrocardiography tracings will be monitored closely for arrhythmias and hypotension following administration of the drug.

PCA's are not routinely used after cardiac surgery, but are often used after other major surgeries including abdominal and orthopedic procedures. The risks of PCA are related to the adverse effects of opioid use, which may include: constipation, nausea/vomiting, sedation, respiratory depression, pruritus,

confusion/hallucination, urinary retention, sweating, miosis and myoclonic jerks. All patients will be monitored closely while using the PCA and if they start showing signs of opioid toxicity, then PCA dosing will be decreased or changed appropriately. If patients show signs of narcotic overdose (respiratory rate < 8 breaths per minute, over-sedation, or muscle rigidity), then naloxone will be administered for opioid reversal.

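### The blind of the injecting surgeon and operating room staff is neither assured nor verified; fixed, disclosed blocks of 4 are a secondary weakness

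*Combined protocol and SAP*

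**What the plan says.** Section III, Parasternal intercostal nerve block, describes saline as transparent and Exparel as translucent. There are two safeguards: the pharmacist supplies a concealed vial, and "sheathed syringes will be used to maintain blinding of the surgeon and operating room staff". Operating room staff transfer the dose from the vial into two syringes. The surgeon then makes ten intercostal injections of 4 mL and infiltrates 10 mL around the drains, 50 mL in all.

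Section IV, in the text after Table 1, adds: "The syringe will be aspirated prior to injection to avoid intravascular injection of the drug". It also counts direct sight of the needle tip as an advantage of the technique.

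Randomization and Blinding lists the investigators, injecting surgeon, operating room staff and ICU and floor staff as blind. The pharmacist alone controls the list. On the sequence: "The subjects will be randomized in blocks of 4 to ensure a 1:1 ratio of placebo to treatment groups".

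On checking the blind: "Subject responses at follow-up regarding speculation about the treatments received will be compared to each subjects actual group assignment". Follow-up puts these questions to patients at the clinic visit about 30 days from discharge. Data Analysis summarises the answers as a percentage correct. No surgeon, operating room or ICU guess is collected.

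**The concern.** The protocol identifies a visible difference between the products and then describes masking for only part of the path from vial to patient. It does not describe the hub, the needle or fluid in the field, and the drawing-up is done by people who are meant to be blind. It also does not explain how an aspirate is inspected in a sheathed syringe. If the contents can be seen, the masking is weakened; if they cannot, the aspiration check is weakened.

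An operator who recognised the fluid would face no stated limit on later involvement. The open routes are these:

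- The first PCA order is written by a member of the study team, and a surgeon-investigator is not excluded (Post-operative pain control).
- ICU stay ends on the judgement of the treating physician and nurses (Secondary outcomes).
- Hospital stay ends at discharge.
- Termination turns on serious adverse events judged related to therapy, and that section does not name who judges (Indications for termination of study).

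A patient guess a month later cannot reveal what the operator saw, and by then it is mixed with whatever pain relief the patient felt. Finally, someone who recognises past fluids and knows the blocks are of 4 can partly predict the next allocation, while eligibility is still being confirmed on the day of surgery.

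**Working it through.** **Masking and its check, step by step**

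- Vial: concealed.
- Transfer to syringe: done by operating room staff who are declared blind; no masking of the transfer is described.
- Syringe: sheathed.
- Hub, needle, injection sites: not described.
- Aspirate: must be checked; how it is seen is not described.
- Verification: patients only, about 30 days after discharge.

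So the documents leave the operator's blind open at the transfer, at the needle and at aspiration, and they contain no measurement that would show a failure.

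**Predictability with blocks of 4**

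The plan gives no figure for this, so there is none to reproduce. Inputs: block size 4 (Randomization and Blinding) and 78 patients (Number of subjects: "The study will include 78 patients, 39 patients in the study drug arm and 39 patients in the control arm"). The recognition rate p is not in the documents, so a range is shown.

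78 = 19 × 4 + 2: 19 full blocks and two patients who open a twentieth.

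*Certain allocations.* The third patient in a block is certain if the first two had the same arm (probability 1/3) and both fluids were recognised (p²). Among the first three patients, two always share an arm, so the fourth is certain if both of those were recognised (p²). Expected number per full block: p²/3 + p² = 4p²/3. The last two patients are never certain.

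- p = 1: 19 × 4/3 = 25.3; 25.3/78 = 32.5%.
- p = 0.5: 19 × 1/3 = 6.33; 6.33/78 = 8.1%.
- p = 0.25: 19 × 0.0833 = 1.58; 1.58/78 = 2.0%.

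*Correct guesses.* Rule: name the arm seen less often so far in the block, and toss a coin on a tie.

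- p = 1: positions 1 to 4 are right with probability 0.5, 2/3, 2/3 and 1, total 2.833. Over the trial, 19 × 2.833 + 0.5 + 0.667 = 55.0; 55.0/78 = 70.5%.
- p = 0.5: 0.5, 0.583, 0.625 and 0.6875, total 2.396. Then 19 × 2.396 + 0.5 + 0.583 = 46.6; 46.6/78 = 59.7%.
- p = 0.25: 55.3% (simulation).

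**Effect on type I error, under an assumed selection shift**

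The plan tests each primary outcome at 0.025 ("Since there are two primary outcomes, we set the type I error at 0.025 for the power analysis"). In 3,000 simulated trials of 78 patients with no treatment effect, patients guessed to be next for Exparel were shifted towards lower scores, and those guessed for placebo towards higher scores, by an assumed amount. The simulation standard error near 0.025 is √(0.025 × 0.975/3000) = 0.003.

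| Recognition | Assumed shift | Rejection rate |
|---|---|---|
| 100% | 0 | 0.023 |
| 100% | 0.1 SD | 0.032 |
| 100% | 0.25 SD | 0.089 |
| 100% | 0.5 SD | 0.285 |
| 50% | 0.25 SD | 0.033 |
| 25% | 0.25 SD | 0.023 |

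**What varying blocks would gain**

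With blocks of 4, 6 or 8 at random and undisclosed, a simple guess from the running imbalance is right 67.9% of the time at full recognition (70.5% for fixed 4) and 53.8% at half recognition (59.7%). This reduces predictability and does not remove it.

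**What an operator guess could show**

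If a share r recognises the fluid and the rest guess at random, the expected share correct is 0.5 + 0.5r. One guess per case gives 78 guesses and, under pure guessing, a standard error of √(0.25/78) = 0.057, so a 95% range of about 39% to 61%. With r = 0.5 the expected share is 75%, well outside that range. Repeated guesses by the same surgeon are correlated, so the range is approximate.

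**The case against.** The strongest reply is that nothing here shows unblinding. A reader might infer that the sheath cannot work. The documents do not support that: they do not describe the sheath, hub or needle, the vial is concealed as well, and the references to direct vision concern nerves, rib spaces and the needle tip rather than the fluid. That stands. What remains is that the blind is not assured and not checked.

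A reader might also infer that the primary outcomes are directly exposed. They are not. The NRS is the patient's own rating, and the NVPS is scored by a provider who is kept blind. The PCA loading dose, bolus, lockout and hourly limit are set out in the protocol, increases are triggered by NRS ≥ 4, and adjustments fall to ICU and floor providers who are also meant to be blind. Some discretion remains in the size of the steps, in titration and in the choice of rescue drug. The Clinical Monitor and the independent safety monitor also review adverse events. This makes the route to bias mainly indirect, but does not close it.

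On the blocks, the worst case needs one person to recognise and track every earlier fluid and also to influence enrolment. Consent precedes randomization, the pharmacist holds the list, day-of-surgery confirmation is assigned to research staff, most eligibility criteria are objective, and more than one surgeon takes part. This stands, and is why the block size is secondary.

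**Conclusion.** The blind of the injecting surgeon and operating room staff is neither assured by the masking described nor verified by any planned check. The passages on sheathed syringes and on aspiration must be reconciled. This rests on the text alone and needs no assumption about how many operators would recognise the fluid.

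The likely harm is indirect: discretionary care, ICU readiness, discharge and adverse-event relatedness. Its size cannot be computed from the documents.

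The block size matters only if masking fails. About 25 of 78 certain allocations (32.5%) and 70.5% correct guesses form an upper bound at full recognition, falling to 8.1% and 59.7% at half. It would be wrong to read the bound as an expected leak, or to conclude that the 0.025 error rate is inflated. Inflation needs an assumed selection shift as well, and at 25% recognition with a 0.25 SD shift none was detectable. The point merits a change because the change costs little and allows the blinding claim to be tested.

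**What to change.** 1. Have the pharmacist, who is already unblinded, dispense the dose in pre-filled sheathed syringes, and state how the hub and needle are masked. Reconcile this text with the aspiration requirement in Section IV.
2. Have the surgeon and operating room staff each record a treatment guess and the reason at the end of the case. No effect on pain has been observed by then, so a guess better than chance points to the fluid and not to efficacy. Report these by arm beside the patients' guesses.
3. Have the pharmacist generate the list with randomly varying block sizes that the protocol does not state. This limits prediction without eliminating it.
4. State that whoever draws up or injects the dose does not score study pain outcomes, write that patient's initial study PCA order or judge adverse-event relatedness. The surgeon's ordinary clinical role is otherwise unchanged.

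Cost: pharmacist preparation time, a one-line form, a new list and a few sentences of protocol text. A surgeon-investigator could not fill those study roles for a patient he or she injected.

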### Cardiac and Neurologic Monitoring

Continuous electrocardiogram (ECG) and vital sign (heart rate, blood pressure, respiratory rate) monitoring will be performed following administration of Exparel®, per standard protocol. Electrocardiogram tracing and vital signs will be documented pre-injection, during injection, post-injection, and at 1 hour and 2 hour post injection. Continuous ECG monitoring will be maintained for at least 48 hours post dose. Vital signs will be measured and recorded at time 0, 2, 4, 8, 12, 24, 36, 48, 60, and 72 hours post dose.

Neurologic assessments will include evaluation for signs of lethargy, restlessness, anxiety, dizziness, tinnitus, blurred vision, tremors and convulsions. Patients will be assessed to the extent possible while still intubated and recovering from anesthesia. The assessments will be performed upon the patient's initial arrival to the ICU (prior to initiation of continuous sedation) and at 2, 4, 8, 12, 24, 36 and 48 hours post dose.

If a subject exhibits signs of suspected bupivacaine toxicity (e.g. cardiotoxic and/or neurotoxic signs or symptoms), then a blood sample will be drawn as soon as possible to determine plasma bupivacaine levels. Cardiovascular system reactions may include atrioventricular block, ventricular arrhythmias and/or cardiac arrest. Central nervous system reactions may include lethargy, restlessness, anxiety, dizziness, tinnitus, blurred vision, tremors and/or convulsions.

### Post-operative pain control

Patients will be treated with fentanyl boluses during the immediate post-operative period and while intubated

in the ICU, until they are able to use the PCA. Pain will be evaluated using the adult NVPS (see Appendix II) and medication will be administered for NVPS score  $\geq 4$ . Per routine cardiovascular ICU protocol, patients will receive Indomethacin 25 mg every 8 hours for three doses if they meet the following criteria: (1) Cr  $< 1.5$  and (2) age  $< 75$ .

The patients will be extubated per the standard cardiovascular ICU protocol (see Appendix IV). Following extubation, pain will be assessed using the NRS (see Appendix II) and pain regimen will be adjusted for NRS score  $\geq 4$ . All patients will receive either fentanyl IV or hydromorphone IV (if fentanyl is poorly tolerated or patient is allergic to fentanyl) via PCA device following extubation. The PCA will be continued for the first 48 hrs postoperatively.

The initial PCA orders will be written by a study team member. If the PCA requires dose adjustment or medication change, then the cardiovascular ICU or floor providers will modify the order per the protocol below. This is a safety mechanism, in case a study team member is unavailable at the time.

The PCA will be set accordingly (see Appendix V):

- A fentanyl PCA will be set up with the following specifications:
  - Loading dose: 1 mcg/kg IV bolus fentanyl divided into 2 doses given 10 minutes apart
  - Bolus dose: 10 mcg IV bolus fentanyl with a lockout interval of 15 minutes and maximum 1 hr limit of 80 mcg. The incremental bolus dose of fentanyl will be increased by 25-50% if analgesia is inadequate (NRS  $\geq 4$ ).
  - If the patient experiences undue side effects from fentanyl PCA (see below) and pain is still inadequately controlled at current dosage, then the patient will be switched over to a dilaudid PCA. However, if pain is controlled with the fentanyl PCA bolus, but the patient is experiencing undue side effects, then the following steps will be taken:
    1. Decrease the PCA bolus dose to 7.5 mcg IV bolus with a lockout interval of 15 minutes.
    2. If the patient still does not tolerate the fentanyl PCA well, then decrease the PCA bolus dose to 5.5 mcg IV bolus with a lockout interval of 15 minutes.
    3. If the patient still does not tolerate the fentanyl PCA well, then decrease the PCA bolus dose to 4.0 mcg IV bolus with a lockout interval of 15 minutes.
    4. If patient continues to not tolerate the fentanyl PCA well, then switch over to a dilaudid PCA.
- If the patient is allergic to fentanyl or continues to poorly tolerate fentanyl (despite dose adjustments), then the patient will be switched over to a dilaudid PCA:
  - Loading dose = 0.02 mg/kg IV bolus hydromorphone divided into 2 doses given 10 minutes apart,
  - Bolus dose = 0.2 mg IV bolus hydromorphone with a lockout interval of 15 minutes and maximum 1 hr limit of 1.6 mg. The incremental bolus dose of hydromorphone will be increased by 25-50% if analgesia is inadequate (NRS  $\geq 4$ ).
- “Poor tolerance” and/or undue side effects of the narcotic may include:
  - Excessive nausea/vomiting refractory to antiemetics.
  - Itching/rash deemed related to narcotic and refractory to Benadryl.
  - Altered mental status or feeling “high” from narcotic bolus.
- The PCA dose may be titrated up or down to attain adequate anesthesia and minimize side effects from the narcotics.
- Naloxone may be used for respiratory depression (respiratory rate  $< 8$  breaths per minute), over-sedation or muscle rigidity secondary to opioid overdose. The PCA bolus dose will be decreased by 25-50% if this occurs.

Following discontinuation of the PCA, patients will be transitioned to Percocet 5/325 mg 1-2 tabs PO every 4 hours as needed or Hydrocodone-Acetaminophen 5/325 mg 1-2 tabs PO every 6 hours as needed.

Rescue pain medication:

- A dose of Toradol 15 mg IV or Tramadol 50-100 mg PO will be administered as rescue medication if patient is still reporting inadequate analgesia ( $NRS \geq 4$ ), but has already met the 1 hour maximum dose of fentanyl or dilaudid.
- Once the patient has been transitioned to PO pain medications, a dose of dilaudid 0.5 mg IV or morphine 2 mg IV may be administered as rescue medication if the patient is still reporting inadequate analgesia ( $NRS \geq 4$ ), but cannot receive additional narcotics (i.e. Percocet or Hydrocodone-Acetaminophen) for that time period.

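### The PCA step-down for opioid side effects ends in a fixed hydromorphone set-up that the protocol's own table rates 3.3 times stronger per bolus, with a new loading dose as printed

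*Combined protocol and SAP*

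**What the plan says.** All of the PCA rules are in section III, Post-operative pain control.

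- **Fentanyl start.** "Loading dose: 1 mcg/kg IV bolus fentanyl divided into 2 doses given 10 minutes apart", then "Bolus dose: 10 mcg IV bolus fentanyl with a lockout interval of 15 minutes and maximum 1 hr limit of 80 mcg".
- **Step-down ladder.** It opens with "if pain is controlled with the fentanyl PCA bolus, but the patient is experiencing undue side effects, then the following steps will be taken". The bolus goes to 7.5 mcg, then 5.5 mcg, and the third step is to "decrease the PCA bolus dose to 4.0 mcg IV bolus with a lockout interval of 15 minutes".
- **End of the ladder.** "If patient continues to not tolerate the fentanyl PCA well, then switch over to a dilaudid PCA".
- **Direct switch.** A patient with undue side effects whose "pain is still inadequately controlled at current dosage, then the patient will be switched over to a dilaudid PCA" does not go through the ladder.
- **Hydromorphone set-up.** "Loading dose = 0.02 mg/kg IV bolus hydromorphone divided into 2 doses given 10 minutes apart", then "Bolus dose = 0.2 mg IV bolus hydromorphone with a lockout interval of 15 minutes and maximum 1 hr limit of 1.6 mg". The lead-in covers patients allergic to fentanyl and those who still tolerate it badly after the dose adjustments.

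Two clauses soften this. The PCA dose may be moved in either direction to balance pain relief against side effects. The bolus is also cut by 25-50% if naloxone is needed for signs of opioid overdose.

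Appendix VI sets 100 mcg fentanyl IV, 1.5 mg hydromorphone IV and 10 mg morphine IV as equal. The section on opioid requirements uses that table to put every narcotic on one scale for the opioid outcome.

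**The concern.** The ladder exists to reduce opioid exposure in a patient who has adequate analgesia but is reacting badly to the drug; the listed reactions include changes in mental state. Its last step goes to a set-up that the protocol's own table rates as stronger than anything on the ladder. The text does not tie the hydromorphone settings to the last fentanyl dose, and it does not exempt switched patients from the loading dose. ICU or floor staff may change the PCA order under the protocol when no study team member is available, so the printed settings may be the ones used.

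There is also a measurement issue. The load is fixed by protocol and body weight, not by what the patient asks for, yet it counts towards cumulative opioid use, which is a primary outcome.

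**Working it through.** **1. The plan's own figure.** From Number of subjects (section II): placebo mean 23.2 mg morphine over 24 h, SD 8.3, a 30% decrease, SD falling in proportion, two-sided alpha 0.025, 39 per arm, 5% dropout.

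- Target difference: 0.30 × 23.2 = 6.96 mg. Treated-arm SD: 0.7 × 8.3 = 5.81 mg.
- At 39 per arm: SE = √((8.3² + 5.81²)/39) = 1.622. Power = Φ(6.96/1.622 − 2.241) = 98.0% (97.6% with the t distribution). The stated 98% reproduces.
- At 37 per arm (39 × 0.95): SE = 1.666 and power = 97.4%.

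**2. The switch on the Appendix VI scale.** 1 mg hydromorphone = 100/1.5 = 66.7 mcg fentanyl = 10/1.5 = 6.67 mg morphine. The hydromorphone bolus is therefore 0.2 × 66.7 = 13.3 mcg fentanyl.

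| Fentanyl bolus before the switch (mcg) | Ratio |
|---|---|
| 4.0 (end of ladder) | 3.33 |
| 5.5 | 2.42 |
| 7.5 | 1.78 |
| 10 (starting bolus) | 1.33 |
| 15 (after one 50% increase) | 0.89 |

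The 15-minute lockout allows four boluses an hour. The most that boluses can deliver rises from 4 × 4.0 = 16 mcg to 4 × 13.3 = 53.3 mcg fentanyl equivalents.

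**3. The load on a switch.** 0.02 mg/kg × 66.7 = 1.33 mcg/kg fentanyl, against 1 mcg/kg for the fentanyl load. The documents give no mean body weight, so weight is assumed:

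- 50 kg: 1.0 mg hydromorphone = 6.7 mg morphine
- 80 kg: 1.6 mg = 106.7 mcg fentanyl = 10.7 mg morphine, which is 46% of 23.2 mg and equal to 106.7/4.0 = 26.7 boluses of 4.0 mcg
- 100 kg: 2.0 mg = 13.3 mg morphine

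The load passes the target difference of 6.96 mg at 6.96/(0.02 × 6.67) = about 52 kg.

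**4. Effect on the outcome, load only.** Assume 80 kg, 37 per arm, all switches within 24 h, and switching unrelated to a patient's other opioid use. With switch rate p and load L = 10.67 mg, an arm's mean rises by pL and its variance by p(1 − p)L².

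| Assumed rate, equal in both arms | Rise in each mean (mg) | Difference (mg) | Power |
|---|---|---|---|
| 0 | 0 | 6.96 | 97.4% |
| 5% | 0.53 | 6.96 | 95.8% |
| 10% | 1.07 | 6.96 | 94.2% |
| 20% | 2.13 | 6.96 | 91.1% |

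With unequal rates, the difference moves by (gap in rates) × 10.67 mg. A gap of 5 percentage points gives 0.53 mg (8% of 6.96), and a gap of 10 points gives 1.07 mg (15%). The shift favours the arm that switches less.

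**The case against.** - **No passage requires an equianalgesic switch.** Appendix VI is called on only to score the outcome, the switch is to a different drug, and its stated ground is intolerance of fentanyl. This stands. A reader might infer a flat safety contradiction, but the text does not contain two instructions that cannot both be followed. It contains an unexplained inconsistency.
- **The dose can be adjusted.** The titration clause is real, but it is permissive and sets no different starting point after a switch, and the load is given in two doses 10 minutes apart. The naloxone clause acts only after an event. Its 25-50% cut leaves 0.10-0.15 mg, or 6.7-10 mcg fentanyl equivalents, still 1.7-2.5 times the 4.0 mcg step.
- **On-demand boluses need not raise the total.** This stands: a larger bolus may be offset by fewer presses. Only the load is certain to add recorded opioid, so the calculation counts only the load.
- **Bias is not shown.** This stands. A reader might infer that the rule inflates the treatment effect on opioid use. The same rules apply in both arms and staff are blinded. If the block works, placebo patients may use more opioid and switch more often. But Table 1 lists nausea and vomiting among the most common reactions to Exparel and pruritus among the common ones, and these overlap with the switch triggers. The documents settle neither the rate nor the direction.
- **The rule might seem to cut dosing when pain is uncontrolled.** The bolus ratio of 0.89 from 15 mcg suggests this, but the same load is given on that route and the hydromorphone bolus may be raised by 25-50%. The documents do not support that reading.
- **The Appendix V flow chart could not be read.** It may say how the load is handled on a switch. If it does, the section text still has to agree with it.

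**Conclusion.** The concern holds as an internal inconsistency with a plausible safety consequence. The bolus ratios and the per-kilogram load follow from the protocol's own figures and need no assumption. The 3.3-fold step applies only to patients who complete the ladder; it does not describe every switch for side effects. For the primary outcome the support is narrower. In a switched patient heavier than about 52 kg, a load that does not reflect demand can exceed the whole difference the trial is powered to detect. Across an arm, the effect depends on switch rates that the documents do not give: equal rates of 5-20% would cost about 2 to 6 points of power at an assumed 80 kg, and bias arises only if the arms switch at different rates.

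**What to change.** The sponsor's clinicians should reconcile the fentanyl ladder and the hydromorphone settings in Post-operative pain control with the Appendix V flow chart and the Appendix VI table. They should state what applies when a patient is switched, including whether the loading dose applies. No dose is proposed here.

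For the analysis, record protocol-fixed loading doses separately from on-demand opioid. Pre-specify one sensitivity analysis that repeats the comparison of cumulative opioid use without the load given on a switch.

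The cost is a wording and order-set amendment, one added data field if the load is not already captured separately (the data storage section mentions only opiate requirements in general), and one extra analysis. No extra patients or procedures are needed.
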